6.4 Duration of Follow-up

Follow-up for serious adverse events and mortality after the single dose of 150 mg of risedronate or placebo is administered will take place during the routine clinic visits during radiation treatment. Radiation treatments will occur within 1 – 3 weeks of taking the study drug. The 30 day follow-up window that is part of mandatory DSMC-SAE reporting will be considered 30 days from the end of all treatments of radiation. This visit can be either a phone call or a visit in person to review adverse events and may be conducted and documented in the medical record by either research study staff RNs or the treating physician. A window of +/- 7 business days is allowed for the 30 day followup assessment.

Specific toxicity related to radiation pneumonitis, radiation fibrosis, and chest wall pain will be collected at each followup point as per appendices K – M.

Patients removed from study for unacceptable adverse events will be followed until resolution or stabilization of the adverse event.

Patients will be followed for a minimum of 3 months for assessment of the primary objective.

Patients will be ideally followed in total for 12 months after completion of radiation therapy for the purposes of this study.

In the event that patients develop progressive disease or a new cancer, requiring additional chemotherapy they will be withdrawn from further study directed followup. In these situations, the followup schedules and imaging become dramatically different from what is directed on this protocol. Additionally further systemic chemotherapy treatments can heavily alter bone density/cortical thickness. As such, if patients develop new disease requiring additional systemic chemotherapy treatment outside of their initial SBRT, they will be withdrawn from study for further follow ups/study directed imaging. Any data that was collected prior to study withdrawal will still be used in analysis. **Immunotherapy or**

hormonal therapy for breast or prostate cancer will not be considered reasons for withdrawal.
Cryoablation or radiofrequency ablation will not be considered a reason for withdrawal from study.

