6.3 Duration of Therapy

The hypothesized bone structural benefit of bisphosphonates with radiation is due to inhibition of early osteoclast activation within as little as 1 week of SBRT. In our preclinical studies, risedronate was only

given just prior to irradiation, and it was not given at all after irradiation was completed. Osteoclast activation only lasted for 1 week post irradiation in rodent models. In non-human primate models, the first follow up scans were performed at 2 months post irradiation, and these scans indicated maximal bone loss had already occurred which was persistent but not worsening on subsequent scans. For this reason, risedronate will be given only once prior to SBRT, at a dose of 150 mg, which is the recommended monthly dose in the setting of osteoporosis in post-menopausal females.

SBRT is given over the course of 3 to 10 treatments and generally this is performed over the course of 1.5 - 2 weeks. Radiation treatments are given every day or every other day Monday through Friday with the exclusion of the weekends or major holidays. In the absence of treatment delays due to adverse events, radiation treatments may continue until the planned treatment dose is reached or until one of the following criteria applies:

- Intercurrent illness that prevents further administration of treatment,
- Unacceptable adverse event(s)
- Patient decides to withdraw from the study

General or specific changes in the patient's condition render the patient unacceptable for further treatment in the judgment of the investigator.

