6.6 Study Calendar

	Baseline Prior to SBRT	Dosing (7- 21 days before SBRT)	During SBRT	1 month Post SBRT	3 ^f months post SBRT	6 ^f months Post SBRT	9 ^f months Post SBRT	12 ^f months Post SBRT
Informed consent	X							
Demographics Medical history History of diabetes Physical exam Performance status Vital signs Height, Weight, M ²		X						
Current Medications list	X				X			
Current or prior use of rank ligand inhibitors, bisphosphonates, and steroids with dates of use and dose as per Appendix G. ^h	X				X	X	X	X
CT chest with or without contrast	X ^a				X	X	X	X
Risedronate or placebo		X ^c						
Urine sample ^d	X				X	X	X	X
Serum Calcium EGFR Serum Creatinine Pregnancy test ^b		X						
Adverse event evaluation (Appendix E)					X			
Specific Radiation Related Chest wall Toxicity (Appendix K)				X ^e	X	X	X	X
Follow up phone call for assessment of adverse events without imaging (Appendix F)				X				
Fracture Incidence (Appendix Q)	X				X	X	X	X
Radiation Treatment Details (Appendix N)			X ^g					

^a Pre-SBRT CT chest scan will be the treatment planning scan. Fracture incidence will be assessed on CT scans

^b Urine pregnancy test (women of childbearing potential) performed within 1 week of treatment planning simulation for radiation.

^c Given once at 7 – 21 days prior to initiation of SBRT

^d For urine sample pick-up and transport, call [name] at [contact] (mobile), [contact] (office). If not available, call [name] at [contact] (mobile).

^e At the 30-Day time point this can be collected over the phone

^f Every 3 month follow-up, and CT imaging will have a window of +/- 8 wks

^g Appendix N may be completed during SBRT but should be completed within 12 weeks of completing SBRT

All pre-study activities must be completed within 12 weeks of the start of study drug including labs

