A growing body of clinical studies has shown that urinary NTx provides a sensitive marker of human bone resorption. Its specificity is based on originating solely from type I collagen, being particularly enriched as a cross-linking structure in bone type I collagen and being produced directly as a proteolytic neoepitope by osteoclast activity during bone resorption. Analysis of urine specimens has certain advantages, including ease of collection and reduced biohazard precautions for clinical laboratory personnel than with bloodbased specimens. However, the obtained results need to be normalized to creatinine.

Principle of Test Method:

The NTX assay is a competitive, enzyme-linked immunosorbent assay (ELISA) for the quantitative measurement of the NTX in human urine. NTX is reported as a normalized ratio to urinary creatinine in order to account for variations in urine flow rate. Therefore NTX and urine creatinine are preferably tested from the same aliquot.

7.5 Evaluable for toxicity:

All patients will be evaluable for toxicity from the time of their first treatment with risedronate, which will be given prior to start of SBRT

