8.2 Adverse Event List for Risedronate

Likely risk and side effects

- Bone and joint pain
- Abdominal discomfort/indigestion

Uncommon/Rare risk and side effects

- Eye pain, redness, swelling, sensitivity to light and or decreased vision
- Glossitis
- Jaw osteonecrosis with pain in the mouth or teeth
- Numbness or feeling of heaviness in the jaw
- Poor healing of gums
- Loose teeth

Very rare

- Allergic and skin reactions
 - Hives, rash with or without blisters
 - Facial/tongue/lip swelling, trouble swallowing or breathing
- Symptoms of low blood calcium (Numbness, tingling, muscle spasms)

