Appendix F – 30 day Treatment Follow-up Form

Study Number: _____ PID: _____

Investigator: M.D. Date: _____ / _____ / _____

Instructions: Complete this form to follow-up with patients for adverse events.

Name of Person Competing form _____

Did the subject have any adverse events in the last 30 days? Yes No

If yes, please describe nature and grade of AE (Note*: If an SAE occurs in this period, report the event as required in [Appendix D](#)):

Was the subject removed from the study by the PI? Yes No

Did the subject withdraw from the study? Yes No

Did the subject complete the full course of SBRT and take the study drug? Yes No

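### Non-serious adverse events in the weeks after the study tablet are not clearly solicited, and the 30-day form's recall does not normally reach back to the tablet

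*Combined protocol and SAP*

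**What the plan says.** - **Start of toxicity evaluation.** Section 7.5 states: "All patients will be evaluable for toxicity from the time of their first treatment with risedronate".
- **Expected drug effects.** Section 8.2 puts two items under its Likely heading: bone and joint pain, and "Abdominal discomfort/indigestion".
- **Timing of the tablet.** Section 6.6, footnote c: "Given once at 7 – 21 days prior to initiation of SBRT".
- **Follow-up after the tablet.** Section 6.4 covers "Follow-up for serious adverse events and mortality after the single dose of 150 mg of risedronate or placebo is administered". The setting it gives is the ordinary appointments held while radiation is under way.
- **30-day contact.** Section 6.4 counts the 30 days from the end of all radiation and allows 7 business days either side. Appendix F then asks: "Did the subject have any adverse events in the last 30 days".
- **Adverse event log (Appendix E).** In the text available for review, the study calendar (6.6) shows one mark for this row, in the 3-month column. The form itself was not available.
- **Recording duty.** Appendix D requires all adverse events to be entered in the institutional system. It defines the intervention period as time on study treatment plus 30 days after the last study treatment.

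**The concern.** The plan puts the period after the tablet in scope for toxicity and names two effects it expects there. Yet the contacts it describes either concern serious events and deaths only or look back over a period that normally starts well after the tablet. A mild symptom that comes and goes before radiation ends would be recorded if the patient mentions it, or if someone asks without being told to.

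At stake is the description of tolerability. The plan itself says that only limited retrospective data exist on anti-resorptive drugs given with SBRT (8.3 and 11.7), so a complete adverse-event profile is one of the useful products of this trial. Early mild events that nobody asked about are hard to recover later.

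There is a second, smaller gap. A patient who takes the tablet but never starts SBRT has no radiation visit and no end-of-radiation date, so neither contact in section 6.4 is ever triggered.

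**Working it through.** **The plan's own figures.** The documents give no figure for adverse-event capture. Their one computed figure is the sample size in 11.4: difference 0.11 mm, SD 0.20 mm, one-sided alpha 0.05, power 0.80. A two-sample t test gives 41.6, rounded up to the stated 42 per group. This point does not affect it.

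**Inputs, with the tablet as day 0**
- Tablet to first fraction: 7 to 21 days (6.1, 6.6).
- Length of SBRT: "generally this is performed over the course of 1.5 - 2 weeks" (6.3), that is 10.5 to 14 days.
- Contact: 30 days after the end of SBRT, plus or minus 7 business days (6.4). Seven business days span 9 to 11 calendar days, depending on weekends.
- Appendix F recall: 30 days.
- 3-month visit: taken as 91 days after SBRT, window plus or minus 8 weeks (56 days) (6.6).

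**Step 1: nominal recall.** Day of contact = gap + SBRT length + 30.
- Shortest: 7 + 10.5 + 30 = 47.5 days. Recall starts at 47.5 − 30 = day 17.5.
- Longest: 21 + 14 + 30 = 65 days. Recall starts at 65 − 30 = day 35.

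The recall period is as long as the interval from the end of radiation to the contact, so a contact made on time looks back exactly to the last fraction and no further.

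**Step 2: with the contact window.** Earliest recall start: 17.5 − 11 = day 6.5. Latest: 35 + 11 = day 46.

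**Step 3: can recall ever reach the tablet?** Only if SBRT ends no more days after the tablet than the contact comes early, at most 11. With the minimum 7-day gap, that leaves 11 − 7 = 4 days from first to last fraction. The fractionation allowed in 6.1 permits this, but it is shorter than the usual course in 6.3 and also needs the contact at the early edge of its window.

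**Step 4: the 3-month evaluation.** Nominally 17.5 + 91 = day 108.5 to 35 + 91 = day 126. With the window, 108.5 − 56 = day 52.5 to 126 + 56 = day 182.

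**Step 5: what remains.** Contact begins at the first radiation visit, day 7 to 21, but 6.4 gives it a content of serious events and deaths only. Appendix D tells staff to enter events they know of; it does not schedule anyone to ask.

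**Step 6: what incomplete capture would do (all rates assumed).** If a fraction c of events is captured equally in both arms, the observed difference is c(p1 − p0) and the risk ratio p1/p0 is unchanged. Power below is for two proportions, 42 per arm, two-sided 0.05, normal approximation with pooled variance under the null.

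| Assumed true rates, placebo vs risedronate | Power, full capture | Power, half of all events captured | Power, only half of the drug-caused excess captured |
|---|---|---|---|
| 5% vs 20% | 55% | 29% | 23% (risk ratio 4.0 to 2.5) |
| 10% vs 30% | 63% | 33% | 25% (risk ratio 3.0 to 2.0) |
| 20% vs 40% | 52% | 25% | 18% (risk ratio 2.0 to 1.5) |

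The table shows the direction of the effect. Nothing in the documents says which row or which capture fraction applies.

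**The case against.** A reader might infer that the plan schedules no adverse-event assessment after the tablet at all. It does not say that. Section 6.4 schedules follow-up of serious events and deaths at radiation visits that begin 7 to 21 days after dosing. Section 6.3 lists unacceptable adverse events among the reasons to stop radiation, so events are expected to be noticed then. Appendix D requires every adverse event to be entered and unplanned admissions of 24 hours or more to be reported whatever their grade. Its 30-day window would also cover a patient whose tablet was the last study treatment. All of this stands. It narrows the gap to active questioning about non-serious events.

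The calendar is weak evidence. The 3-month column is the midpoint of a cell that would span Dosing to 12 months, so the single mark may be a merged cell lost in text extraction. Appendix E was not available, and section 10.0 refers to a pre-filled log, which might list the relevant symptoms or run from dosing. This also stands, so the point is made to rest on 6.4 and Appendix F, which do not depend on the table.

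A reader might also infer that most of the expected drug effects will be missed and that the arms will look falsely alike. The documents support neither. They give no onset, duration or frequency for these effects, so no count of missed cases can be derived. Under double-blinding, under-capture is probably similar in both arms. That shrinks the absolute difference and the power but does not by itself change the risk ratio. Section 11 plans no general tolerability comparison, and in the assumed examples 42 per arm has only 52% to 63% power even with full capture.

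**Conclusion.** The point holds in a limited form. Followed exactly, the Appendix F look-back and its end-of-radiation anchor leave roughly the first 18 to 35 days after the tablet outside recall (6.5 to 46 days with the contact window). Section 6.4 does not name non-serious events for that interval. This sits badly with 7.5, which starts toxicity evaluation at the tablet. Tolerability of the randomised drug may be under-ascertained and absolute differences between arms attenuated; by how much cannot be determined from the documents.

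The day counts assume the usual SBRT length in 6.3 and calendar equivalents of 9 to 11 days for the contact window. The conclusion would weaken if the Appendix E form already runs from dosing and is completed during SBRT, which should be checked against the original PDF. No primary or secondary objective and no sample-size figure is affected. It is a worthwhile, inexpensive improvement and does not threaten the trial's main result.

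**What to change.** 1. **Appendix F.** Replace the 30-day look-back with a question covering the time since the study drug was taken, or since the last adverse-event assessment if there was one.
2. **Section 6.6.** Mark Appendix E at the first SBRT visit, asking blinded patients about all adverse events back to the tablet date. Confirm in the calendar which other visits the Appendix E row is meant to cover.
3. **Section 6.4.** Name non-serious events alongside serious ones, and count the 30-day contact from the tablet date for anyone who takes the tablet but never starts SBRT. This gives Appendix D's existing reporting window a contact to go with it.
4. **Section 7.5 (minor).** Refer to study drug (risedronate or placebo), so that the starting point is defined in both arms.

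Cost: changes to protocol and form wording, one short question at a visit that already takes place, an occasional phone call, and more low-grade events to enter. Dose, endpoints, sample size and analysis stay as they are.

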During protocol intervention is considered to be the time period while a patient is on study treatment or during the time period within 30 days of last study treatment (even if patient begins a new (non-study) treatment during the 30 days). This window of 30 days should be the standard window to be used in all protocols unless a specific scientific rationale is presented to suggest that a shorter window can be used to identify events. If it is a trial sponsored by Industry and the sponsor requires a longer window for monitoring of SAEs, then the longer window of time specified by the sponsor should be followed.

What is considered as an Unexpected Grade 4 event?

Any grade 4 event that was not specifically listed as an expected adverse event in the protocol should be considered as unexpected. A grade 4 adverse event can be considered to be unexpected if it is an event that would not be expected based on the treatment being received or if it is unexpected based on the health of the patient. In either case, if there is any uncertainty about whether a grade 4 adverse event is expected or unexpected it should be reported to DSMC.

DSMC notification responsibilities of the person (e.g., nurse) handling the reporting/documenting of the SAE in WISER:

1. Make a phone call (or speak in person) to the appropriate clinical member of the DSMC according to the schedule as listed below (page if necessary).
2. Enter a new SAE into the SAE module that is located in the Subject>> CRA Console in WISER **WITHIN 24 HOURS** of first knowledge of the event. Information can be entered and saved, but the DSMC members will not be notified until a date is entered into the DSMC Notification Date Field. This will ensure that all persons that need to be made aware of the event (i.e., PI, study team members and DSMC members) will be notified; remember to file a copy of the confirmation.
3. Document that the appropriate person(s) on the DSMC has been contacted. Indicate the name of the DSMC clinician that was contacted and the date and time contacted in the Event Narrative field in the SAE console of the particular subject.
4. Document whether or not the protocol should be suspended based on the discussion with the DSMC clinician. This is the major function of the email notification. Enter whether the protocol should be suspended in the Event Narrative Field.

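### The 30-day adverse event contact may take place 9-10 calendar days before the 30-day SAE reporting window closes, and a late contact asks about the wrong 30 days

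*Combined protocol and SAP*

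**What the plan says.** Section 6.4 (Duration of Follow-up) defines the window for mandatory DSMC SAE reporting: it "will be considered 30 days from the end of all treatments of radiation". The same paragraph provides for a contact, by phone or in person, to review adverse events, and adds: "A window of +/- 7 business days is allowed for the 30 day followup assessment". It does not ask for a second contact if the first takes place before day 30.

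Appendix D counts an event as reportable if it occurs on study treatment or "during the time period within 30 days of last study treatment". On the length of that period it says: "This window of 30 days should be the standard window to be used in all protocols unless a specific scientific rationale is presented". The events concerned are unexpected grade 4 events, unplanned hospital stays of at least 24 hours whatever the grade, and deaths.

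Appendix F, the form completed at the contact, asks: "Did the subject have any adverse events in the last 30 days".

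In the study calendar (6.6) the next scheduled visit is at 3 months, with this footnote: "Every 3 month follow-up, and CT imaging will have a window of +/- 8 wks".

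**The concern.** A contact meant to review a 30-day period can do so completely only if it takes place at or after the end of that period and looks back to its start. The plan guarantees neither. The minus side of the visit window lets the contact precede day 30, and the fixed 30-day look-back on the form moves with the contact date. The two match the reporting window exactly only when the contact falls on day 30.

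What is at stake is when, and how actively, the trial learns of reportable events in part of its own safety window. These are outpatients once radiation ends, and a hospital stay elsewhere may not be known to the study team until someone asks. Sections 8.3 and 11.7 describe the safety data on this combination as limited and retrospective, so actively covering the whole window is a reasonable aim. How much of it is covered should not depend on the day the call happened to be made.

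**Working it through.** The plan states no calculated figure on this point, so the check is a calendar count.

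**Inputs**
- Reporting window: day 0 (last fraction) to day 30 (6.4, Appendix D).
- Contact window: 7 business days either side of day 30 (6.4).
- Weekday of the last fraction (6.3): "Radiation treatments are given every day or every other day Monday through Friday".
- Look-back on the form: 30 days before the contact (Appendix F).
- 3-month visit: +/- 8 weeks (6.6). Taking 3 months as 91 days is my assumption.

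**Contact limits.** Because 30 = 4 x 7 + 2, day 30 falls two weekdays after the weekday of the last fraction. Counting 7 weekdays back and forward from it, with no holiday, gives:

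| Last fraction | Day 30 | Earliest contact | Days before day 30 | Latest contact | Days after day 30 |
|---|---|---|---|---|---|
| Mon | Wed | day 21 | 9 | day 39 | 9 |
| Tue | Thu | day 21 | 9 | day 41 | 11 |
| Wed | Fri | day 21 | 9 | day 41 | 11 |
| Thu | Sat | day 21 | 9 | day 40 | 10 |
| Fri | Sun | day 20 | 10 | day 39 | 9 |

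**Early side.** Days not covered = 30 - contact day = 9 or 10, which is 9/30 = 30% to 10/30 = 33% of the window. An early gap of 11 days would need day 30 to fall on a Monday or Tuesday, which a Monday-to-Friday schedule rules out, or a holiday in the span. One holiday can stretch the gap to between 10 and 12 days, depending on the weekday.

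**Late side.** Start of the look-back = contact day - 30. At the latest contact this is 39 - 30 = 9 to 41 - 30 = 11. The question as worded therefore leaves out roughly the first 9-11 days after radiation, or 30% to 11/30 = 37% of the window.

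**Next scheduled contact.** 91 - 56 = day 35 and 91 + 56 = day 147. As an illustration, an event on day 25 after a compliant day-20 call would next be asked about between 35 - 25 = 10 days and 147 - 25 = 122 days after it happened. These are the extremes of the allowed window, not typical delays.

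**After the fix.** With a contact allowed from day 30 to +7 business days, the earliest is day 30 and the latest is day 39-41, so no tail is left out. The form question must change as well, because a 30-day look-back from day 39-41 would still miss the start.

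**The case against.** Several stronger conclusions are tempting, and the documents do not support them.

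- **A reader might infer that the last days of the window go unassessed.** They do not necessarily. Only the contact date floats. Appendix D obliges any team member who becomes aware of a qualifying event within 30 days to report it, and the calendar shows a later adverse event evaluation, apparently at 3 months (the table layout leaves the column somewhat uncertain). The content of the Appendix E log was not available for this check. What remains is that both the awareness duty and the later visit are passive or late for this period.
- **A reader might infer that Appendix D is breached because the window is shortened without a rationale.** Its requirement concerns the reporting period, which 6.4 keeps at 30 days. A visit tolerance is a different thing.
- **A reader might infer that the 24-hour entry rule is defeated.** That clock starts at first knowledge, so an event learned of late can still be entered on time. What is delayed is committee review.
- **The late-side gap rests on a literal reading of one question.** Section 6.4 sets no look-back limit, and staff may well ask more widely. That is fair, but the form is what standardises the question.
- **The randomised agent is a single dose given 7-21 days before SBRT.** With three consecutive daily fractions, a day-20 contact is at least 7 + 2 + 20 = 29 days after the dose. The uncovered tail therefore mostly concerns events after standard radiation. This lowers the stakes, but the protocol chose to anchor its safety window to the end of radiation.

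On the other side, the 3-month visit is not a backstop for everyone. Section 6.4 withdraws patients who need new systemic chemotherapy from further study-directed follow-up, while Appendix D keeps events reportable for 30 days even if other treatment begins. A patient called early and then withdrawn may have no later scheduled study contact.

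**Conclusion.** The point holds as a minor one. The 30-day contact may compliantly take place on day 20-21, leaving 9-10 calendar days (30-33%) of the reporting window to passive reporting or to a visit that may fall anywhere from about day 35 to day 147. A contact at the late limit, with the form read literally, does not ask about roughly the first 9-11 days (30-37%). The two gaps are alternatives for a given patient, not additive, and both are the worst case that the window permits.

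The consequence is delayed or incomplete active ascertainment. It is not a shortened reporting period or a breach of reporting rules. The same window applies to both blinded arms, and the primary endpoint, its analysis and the sample size are untouched. The figures assume Monday-to-Friday fractions, no holiday in the span, and 3 months taken as 91 days.

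**What to change.** Make two changes together:

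1. In 6.4, make the window one-sided: not before day 30 after the last fraction, up to +7 business days.
2. On Appendix F, replace the fixed 30-day look-back with a question about events since the end of radiation or since the last assessment, so that a late contact still covers the whole period.

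The cost is one line in each place and slightly less scheduling flexibility, for a contact that may already be made by phone.
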